Multicenter double-blind placebo-controlled randomized parallel group clinical study of efficacy and safety of MMH-MAP in the treatment of cognitive disorders in patients with ischemic stroke in the carotid arteries

Phase III

Sponsor

OOO «NPF «MATERIA MEDICA HOLDING»

Protocol number Version date:

ClinicalTrials.gov Id:

MMH-MAP-002 June 11, 2019 NCT04295681

Protocol Summary

This document represents the protocol summary for the study on human subjects. The study will be carried out in accordance with ICH GCP, National Standard of the Russian Federation GOST 52379-2005 "Good Clinical Practice", World Medical Association Declaration of Helsinki, relevant requirements of the regulatory authorities as well as the study procedures.

Title of Study

Multicenter double-blind placebo-controlled randomized parallel group clinical study of efficacy and safety of MMH-MAP in the treatment of cognitive disorders in patients with ischemic stroke in the carotid arteries.

Phase: III

Sponsor: Company «MATERIA MEDICA HOLDING», Moscow, Russia *Protocol No.* MMH-MAP-002

Purposes of the study

- To evaluate efficacy of MMH-MAP in the treatment of cognitive disorders in patients with ischemic stroke in the carotid arteries.
- To evaluate the safety of MMH-MAP in the treatment of cognitive disorders in patients with ischemic stroke in the carotid arteries.

Endpoints

Primary endpoint

1. Average MoCA score on treatment day 90.

Secondary endpoints

- 1. Changes in NIHSS score on treatment day 12, 90.
- 2. Percentage of patients with no major disability (mRs 0-1) after 90-day therapy.
- 3. Therapeutic and adverse effects, efficacy index according to clinical global impression scale (CGI-EI) after 90-day therapy.

Safety assessment

- Percentage of patients with sequelae of cerebral infarction (severe infections hospitalacquired pneumonia, uroinfection; deep venous thrombosis, PATE; epileptic episodes) during IMP therapy.
- Frequency of all-cause mortality outcomes during IMP therapy.
- Percentage of patients with recurring cerebral infarction during IMP therapy.
- Occurrence and nature of adverse events (AEs) during the treatment, their intensity (severity), relation to the study drug, outcome.

- Changes in vital signs during IMP therapy.
- Percentage of patients with clinically relevant abnormal laboratory tests during IMP therapy.

Study design

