The study included two interim analyses: on 15 and 30 percent of the recruited patients. Distribution of the first type error in accordance with the O'Brien–Fleming error waste function, of the second type – in accordance with the Pocock function. It is possible to stop the study early due to both acceptance and rejection of the null hypothesis. The interim analysis is based on the data obtained from the results of examination and treatment of the number of patients established by the protocol who completely completed participation in the study. Number of patients for the first interim analysis: 30 patients (MMN-MAP group - 15 patients, Placebo group - 15 patients). Number of patients for the second interim analysis: 60 patients (MMN-MAP group - 30 patients, Placebo group - 30 patients). Number of patients for the final analysis: 196 patients (MMN-MAP group - 98 patients, Placebo group - 98 patients).

Treatment

Group 1

Name of the medicinal product: MMH-MAP

Active ingredient: Modified affinity purified antibodies to S100 brain-specific protein - 0.006 g*.

* applied onto lactose monohydrate as a water-alcohol mixture containing no more than 10^{-391} ng/g active form of the API

Excipients: Lactose monohydrate - 0.267 g

Microcrystalline cellulose - 0.030 g

Magnesium stearate - 0.003 g

Method of administration: Tablet for oral use. 2 tablets twice daily (approximately at the same time), outside the meal (between meals or 15 minutes before meals or fluids). Keep the tablets in mouth until completely dissolved.

Dosage form: Tablets.

Description: Flat cylinder-shaped scored beveled edge white to off-white tablets with a smooth, uniform surface.

Storage conditions: At temperature ≤ 25 °C.

Group 2

Name of the medicinal product: Placebo

Active ingredient: No

Excipients: Lactose monohydrate - 0.267 g

Microcrystalline cellulose - 0.030 g Magnesium stearate - 0.003 g

Method of administration: Tablet for oral use. Dose per administration: 2 tablets. 2 tablets twice daily (4 tablets/day). The tablets should be held in mouth without chewing until complete dissolution.

Dosage form: Tablets.

Description: Flat cylinder-shaped scored beveled edge white to off-white tablets with a smooth, uniform surface.

Storage conditions: Store at a temperature not exceeding 25 ° C.

Treatment duration

MMH-MAP/Placebo treatment duration is 90 days.

Observation period

In total the patients will be monitored for 90 days.

Hospital stage - 12 days;

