Medical history	+			
Concomitant conditions and diseases	+			

Physical examination	+	+		+
Evaluation of vital				
signs (HR, RR, BP) ***	+	+		+
Recording therapy for				
concomitant diseases	+	+	+	+
Filling MoCA scale	+			+
Filling Glasgow scale	+			
Filling NIHSS scale	+	+		+
Filling mRs scale	+			+
Pregnancy test	+			
Safety laboratory tests	+			+
Inclusion/exclusion	+			
criteria				
Randomization	+			
Dispensing of study	+	+		
drug				
Study drug				
accountability and		+		+
return				
Treatment compliance		+		+
Evaluation of study	Ŧ	Ŧ	Т	–
treatment safety	т	Ŧ	Ŧ	т
Filling CGI-EI scale				+
Visit completion	+	+	+	+
Study completion				+

* The end of the inpatient period is the last day of hospitalization for the current stroke

** Study completion

**** HR - heart rate; RR - respiration rate; BP - blood pressure

Statistical Analyses

Samples

Total set includes all the subjects who have signed ICF. This sample will consider all adverse events (AEs) throughout the study, including those occurred prior to the study therapy.

The sample including all patients who received at least one dose of the study drug to be used for *analysis of the study treatment safety and tolerability* (*Safety population*), as all AEs identified after the study drug administration will be recorded.

Full Analysis Set This sample will consist of all enrolled patients, except for those who met at least one of the following criteria:

- 1) non-compliance with inclusion/exclusion criteria;
- 2) patient did not take any dose of study drug;
- 3) absence of any patient data after administration of study drug.

This was the best set for the Intention-to-treat method, so it will be used in the Intention-to-treat

efficacy analysis (ITT-analysis) of the study therapy.

Per Protocol set. This sample includes all patients who received full protocol therapy and completed all scheduled visits. This set will be used for *Per Protocol analysis (PP analysis) of efficacy of study therapy. Per Protocol set* will not include the patients whose data are fully or partially invalid for analysis due to a protocol deviation.

Protocol deviations resulting in full or partial data invalidity:

- 1. Violation of visit schedule.
- 2. Inappropriate distribution/issue of the study drug.
- 3. Prescription of prohibited therapy.
- 4. Increase or decrease of 25% or more in the amount of study therapy received.

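### The on-therapy window for death, recurrent infarction and stroke sequelae is undefined and, read literally, drops events that follow early stopping of study drug

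*Combined protocol and SAP*

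**What the plan says.** Under Safety assessment, the three clinical-event endpoints share one limit:

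- Death: "Frequency of all-cause mortality outcomes during IMP therapy".
- Recurrent stroke: "Percentage of patients with recurring cerebral infarction during IMP therapy".
- Sequelae of cerebral infarction: a list of complications ending "deep venous thrombosis, PATE; epileptic episodes) during IMP therapy".

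The adverse-event endpoint has a similar limit: "Occurrence and nature of adverse events (AEs) during the treatment". None of these phrases is defined.

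Other sections bear on the window:

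- Treatment duration is 90 days. Under Observation period, "In total the patients will be monitored for 90 days".
- Under Statistical Analyses, Samples, the Total set considers adverse events over the whole study. The Safety population is justified by a recording rule with no end at the last dose: "as all AEs identified after the study drug administration will be recorded".
- Criteria for Withdrawal or Termination include an adverse event that requires stopping study drug (item 4) and a need for prohibited medication (item 3).
- The visit descriptions and the Schedule of study procedures show a phone visit around Day 45 and a final visit around Day 90. They show no early-termination visit and no contact with a patient who has stopped or withdrawn.

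**The concern.** A count that ends at the last tablet depends on something that happens after randomisation and may be related to outcome. The plan itself makes that link. Epileptic episodes are a listed sequela, antiepileptic agents are on the prohibited list, and needing a prohibited medication is a withdrawal criterion. A patient can therefore have a counted complication, meet a withdrawal criterion because of it, and then die or have a second infarction outside the counting window. The same path runs through any adverse event that leads to discontinuation.

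Two things are at stake. First, the named endpoints may undercount the most serious events. Second, if the arms stop at different rates, they are undercounted by different amounts, and the arm with more early stopping can look safer. An all-cause mortality figure limited in this way no longer compares the groups as treated from first dose over a common period.

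**Working it through.** **1. Does the plan's sample size depend on this?** Inputs from Evaluation of sample size: difference 1.3, SD 3.0, two-sided alpha 0.05, power 80%, looks at 0.15, 0.30 and 1 of the information.

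- Fixed design: 2 × (1.960 + 0.842)² × 3.0² / 1.3² = 83.6 per group, so 84.
- The three-stage boundaries in the plan's code, solved numerically, inflate this by 1.167: 83.6 × 1.167 ≈ 97.5, so 98 per group, as stated.
- Withdrawal: 98 / (1 − 0.2) = 122.5, so 123 per group and 246 in total, as stated.

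The calculation rests on MoCA alone. Changing the safety window alters none of it.

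**2. What do the two readings of the window give?**

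| Patient | Window ends at last tablet | Window is the planned 90 days |
|---|---|---|
| Takes tablets to Day 90 | All events to Day 90 counted | The same |
| Stops early, event before stopping | Counted | Counted |
| Stops early, event after stopping | Not counted in the three endpoints | Counted, if anyone collects it |

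The readings differ only in the last row. Even the wider reading needs follow-up that is not described.

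**3. How much follow-up is in the last row?** The documents give no stopping times, so both inputs below are assumed. With k patients stopping at mean day m, the share of patient-days outside the window is k × (90 − m) / (246 × 90), with denominator 22,140.

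| Share stopping (k) | Mean Day 75 | Mean Day 45 | Mean Day 15 |
|---|---|---|---|
| 10% (25) | 375, 1.7% | 1,125, 5.1% | 1,875, 8.5% |
| 20% (49) | 735, 3.3% | 2,205, 10.0% | 3,675, 16.6% |
| 30% (74) | 1,110, 5.0% | 3,330, 15.0% | 5,550, 25.1% |

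The plan's 20% does not fix the middle row as the expected case. It inflates the number signing consent, and the withdrawal list includes screening failure and eligibility error, so 49 is not a count of patients who stop tablets.

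**4. What could that mean in events?** Assume a 5% event risk over 90 days, with 49 of 246 stopping at a mean of Day 45.

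- Counted: 197 × 0.05 + 49 × 0.05 × 45/90 = 9.85 + 1.225 = 11.1.
- Uncounted, risk unchanged after stopping: 49 × 0.05 × 45/90 = 1.2, which is 1.2 of 12.3 (10%).
- Uncounted, risk three times higher after stopping: 3 × 1.225 = 3.7, which is 3.7 of 14.8 (25%).

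The uncounted share does not depend on the 5%, which cancels.

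**5. Can it distort the comparison?** Assume both arms have a true 5% risk, unchanged by stopping, and that 10% of one arm and 30% of the other stop at a mean of Day 45. The literal count gives 5% × (1 − 0.10 × 0.5) = 4.75% against 5% × (1 − 0.30 × 0.5) = 4.25%. The arm with more stopping looks better although the risks are equal. The gap is small here; it grows if stopping is earlier or risk rises afterwards.

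**The case against.** The strongest reply is that the phrase may simply mean the planned treatment period. Treatment and observation are both 90 days, and the same qualifier is attached to vital signs and laboratory tests, which are scheduled at the final visit around Day 90. On that reading nothing is cut off. This is plausible, but the documents do not settle it, and the fix would then only make the intention explicit.

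Second, late events need not vanish. The adverse-event sets have no last-dose cut-off, and the adverse-event endpoint includes each event's outcome. A fatal outcome of a pneumonia that began on drug could appear there. This stands, and it rules out a reading that a reader might infer: that the trial's safety question is answered only for time on drug. It does not repair the named endpoints. Analysis-set descriptions do not redefine them, and adverse-event tables by severity, seriousness and relationship do not replace a mortality or recurrence count.

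Third, rewording recovers no data if a patient who meets a withdrawal criterion leaves the study. That is correct, and it is why the change needs a contact as well as a definition. The document calls itself a summary, so a follow-up rule may exist elsewhere; the point is that none is described here.

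Fourth, the withdrawal list also covers patient preference, pregnancy and joining another trial. It cannot be claimed that the uncounted days belong to the sickest patients, only that some stopping is tied to complications.

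**Conclusion.** The point holds in a limited form. Three safety endpoints carry an undefined on-therapy window. Read literally, they omit events after early stopping, the window does not match the adverse-event sets or the 90-day observation period, and the plan's own withdrawal rules can make stopping informative.

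The size is unknown. The range of 1.7% to 25% of patient-days rests on assumed stopping of 10% to 30% at a mean of Day 75 to Day 15; the event counts rest further on an assumed 5% risk and an assumed ratio of 1 or 3 after stopping. No single figure in that range should be quoted as the expected loss. Patients who complete 90 days of tablets are unaffected, and so is the sample size.

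Two stronger readings are not supported. One is that the plan sets a 90-day safety objective and fails it. The safety purpose, "To evaluate the safety of MMH-MAP in the treatment of cognitive disorders in patients with ischemic stroke in the carotid arteries", names no horizon; the 90 days comes from the treatment and observation periods. The other is that deaths drop out of the secondary endpoint "Percentage of patients with no major disability (mRs 0-1) after 90-day therapy". The documents do not say how a patient who dies is scored, and that silence does not show exclusion.

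**What to change.** - In the Safety assessment list, define all-cause death, recurrent cerebral infarction and the listed sequelae as occurring *from first dose to Day 90, whether or not study drug is still being taken*, analysed in the Safety population.
- Keep the on-therapy count of the same three endpoints as a supplementary table, and state when that window ends.
- State that patients who stopped study drug, and have not withdrawn consent to contact, are phoned at Day 90 for vital status and stroke-event status. Report how many in each arm could not be reached.

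The cost is endpoint wording, one extra table, and a phone contact of the kind already used at Visit 3, for early stoppers only. The sample size is unchanged at 98 per group and 246 in total.

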Design: double-blind, randomized, parallel group placebo-controlled clinical study of efficacy and safety of MMH-MAP in the treatment of cognitive disorders in patients with ischemic stroke in the carotid arteries.

The study will enroll hospitalized subjects of either gender aged 40-75 years old with verified diagnosis of ischemic stroke in the carotid arteries within 72 hours post debut having moderate cognitive disorders, moderate neurological deficit.

At Visit 1 (day 1) the subject's complaints and medical history will be collected, objective examination, safety laboratory tests (hematology, serum chemistry, urinalysis) will be performed. The investigator will evaluate the patient's level of consciousness using The Glasgow Coma Scale, intensity of cognitive disorders using The Montreal Cognitive Assessment (MoCA), condition using National Institute of Health Stroke Scale (NIHSS) and The Modified Rankin Scale (mRs). Concomitant therapy will be recorded and changes in cerebral CT/MRI will be evaluated. If the subject meets inclusion criteria and has no exclusion criteria, he/she will be randomized to MMH-MAP or Placebo group. The first dose of the study product should be taken within 72 hours post stroke debut.

At Visit 2 (day 12±3, end of hospitalization period - the last day of hospitalization due to the current stroke) complaints will be collected, objective examination findings will be recorded, monitoring of the prescribed and concomitant therapy will be performed, treatment safety, compliance and stroke severity according to NIHSS will be evaluated.

By the end of hospital therapy the subject will be switched to outpatient therapy with continuation of IMP and medical assistance designed for the treatment of stroke and its sequelae. At Visit 3 (day 45±7 days) the investigator will make a phone call to the subject evaluating the treatment safety.

At final Visit 4 (day 90±7 days) complaints will be collected, objective examination findings will be recorded, monitoring of the prescribed and concomitant therapy will be performed, treatment safety, compliance, condition according to NIHSS will be evaluated, mRs, Clinical Global Impression Efficacy Index (CGI-EI) will be filled. The investigator will perform MoCA testing. Safety laboratory tests (hematology, serum chemistry, urinalysis) will be carried out.

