- 12. Malabsorption syndrome, including congenital or acquired lactase deficiency (or any other disaccharidase deficiency) and galactosemia.
- 13. Any conditions which, according to the investigator opinion, may interfere with the subject's participation in the study.
- 14. Prior history of non-adherence to a drug regimen, a psychiatric disorder, alcoholism or drug abuse, which, in the opinion of the investigator, can compromise compliance with study protocol.
- 15. Pregnancy, breast-feeding; childbirth less than 3 months prior to the inclusion in the trial, unwillingness to use contraceptive methods during the trial.
- 16. Participation in other clinical studies within 3 month prior to enrollment in the study.
- 17. Patients who are related to any of the on-site research personnel directly involved in the conduct of the trial or are an immediate relative of the study investigator. 'Immediate relative' means husband, wife, parent, son, daughter, brother, or sister (regardless of whether they are natural or adopted).
- 18. Patients who work for OOO "NPF "Materia Medica Holding" (i.e. the company's employees, temporary contract workers, designated officials responsible for carrying out the research or any immediate relatives of the aforementioned).

Criteria for Withdrawal or Termination

- 1. Screening failure.
- 2. Inability or patient's refusal to comply with the protocol requirements.
- 3. Necessity in medications prohibited within the study.
- 4. An adverse event requiring discontinuation of the study drug.
- 5. Eligibility error.
- 6. Patient's desire to complete the study early for any reason.
- 7. Pregnancy.
- 8. Participation in any other clinical trial.
- 9. Cases not covered by the protocol where the investigator believes that the patient's continued participation in the study is harmful to him.

Number of subjects

It is planned to include 246 subjects, which is expected to yield at least 196 patients (98 x 2 groups - MMH-MAP and Placebo) completing all protocol procedures.

Interim analysis

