- 5. Inability to assess patient's objective compliance (adherence to therapy) according to the formula (e.g. loss of packaging).
- 6. Gross inconsistencies between source documents and CRF detected during monitoring or other authorized inspection.
- 7. Violations of the Informed consent procedure.
- 8. Non-compliance with the clinical study protocol procedures.
- 9. Inability to collect all patient's data used for evaluation of the study endpoints (e.g. lack of entries in source documents required for verification of inclusion/exclusion criteria, safety and efficacy criteria).
- 10. Other protocol deviations resulting in full or partial data invalidity.

Data treatment and all statistical calculations under the protocol will be made using SAS-9.4 statistical software.¹

Evaluation of sample size

The sample size was assessed in accordance with the following rules and assumptions:

- 1. Statistical assumptions:
 - 1.1 the power of statistical tests 'P = (1β) ' is 80% (the probability of correct rejection of the null hypothesis is 0.8)
 - 1.2 the probability of type 1 error 'a' is less that 5% (the probability of false acceptance of the alternative hypothesis is less than 0.05)
 - 1.3 statistical criteria of intergroup comparisons are two-sided, unless otherwise stated
 - 1.4 calculation of sample size will be based on the assumptions on the expected effect declared in the primary efficacy criterion of the protocol

¹ Holder of license: OOO "NPF "Materia Medica Holding", No. 70100045.

Protocol No. MMH-MAP-002 11-Jun-2019

- 1.5 ratio between sample sizes of MMH-MAP and Placebo sample sizes is 1:1 (1 MMH-MAP patient per 1 Placebo patient)
- 1.6 statistical hypotheses null and alternative hypotheses on the difference between study drug and placebo under the dosing regimen used:

H₀: $\mu_1 - \mu_2 = 0$ H_a: $\mu_1 - \mu_2 \neq 0$

where μ_1 - change in mean MoCA summary score in MMH-MAP group, μ_2 - change in mean MoCA summary score in Placebo group

1.7 calculation of sample size for statistical criteria was made using the following program code:

Proc seqdesign errspend Design nstages = 3 Info = cum (0.15,0.3,1) Method (alpha) = UNI (rho = 0.5 tau = 0) Method (beta) = UNI (rho = 0 tau = 0) Stop = both Alpha = 0.05 Beta = 0.2 Samplesize model = twosamplemean (meandiff = 1.3 stddev = 3.0) Run

1.8 terminal sample size will be determined using the formula:

$$N_T = N_{PP}/(1 - K_{\rm B})$$

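### Events that stop study drug are listed as reasons for withdrawal, and no later assessment is described, so a Full Analysis Set patient can have no Day-90 MoCA and no stated rule for analysis

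*Combined protocol and SAP*

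**What the plan says.** - **Withdrawal.** Under Criteria for Withdrawal or Termination, item 3 is "Necessity in medications prohibited within the study" and item 4 is "An adverse event requiring discontinuation of the study drug". They share one list with refusal, pregnancy and the patient's wish to finish early. Stopping drug is not separated from leaving the study, and no early-termination visit or off-drug assessment is described.
- **Timing of MoCA.** The primary endpoint is mean MoCA at Day 90. The Schedule of study procedures marks MoCA at Visits 1 and 4 only. At Visit 2, "compliance and stroke severity according to NIHSS will be evaluated", without MoCA. Visit 3 is a phone call. For Visit 4 the Study design section says "The investigator will perform MoCA testing".
- **Analysis sets (Statistical Analyses, Samples).** The FAS, used for the intention-to-treat analysis, leaves out ineligible patients, undosed patients and those with "absence of any patient data after administration of study drug". For the Per Protocol (PP) set: "This sample includes all patients who received full protocol therapy and completed all scheduled visits". Item 9 of the deviations that invalidate PP data is "Inability to collect all patient's data used for evaluation of the study endpoints". The summary does not say whether FAS or PP is primary.
- **Interim analysis.** Both looks (30 and 60 patients) use patients "who completely completed participation in the study". The final analysis is set at 196, which Number of subjects gives as the expected count of completers.

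**The concern.** A patient who stops drug after Visit 2 for an adverse event has post-dose data and so belongs to the FAS. If withdrawal ends follow-up, that patient has a baseline MoCA and nothing later. The outcome is then lost because of an event after randomization, and no analysis can recover a value that was never collected.

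Some of this loss could plausibly be related to outcome. The safety section lists epileptic episodes among the sequelae to be counted, antiepileptic agents are prohibited, and need for a prohibited medicine is a withdrawal criterion.

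The final estimate and both stop-or-continue decisions would then rest on a group selected after randomization. The summary states no analysis that would detect or bound the effect of that selection.

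**Working it through.** **1. The plan's own figure.** Inputs from Evaluation of sample size, item 1.7: two-sided alpha 0.05, beta 0.20, difference 1.3, SD 3.0, information fractions t = 0.15, 0.30, 1, stopping for both acceptance and rejection. The boundaries are: reject if |Z| ≥ Ca·t^(-0.5), accept if |Z| < (Ca + Cb)·t^0.5 − Cb.
- Numerical integration gives Ca = 1.874, Cb = 1.152, drift 3.026.
- N = 4 × 3.0² × 3.026² / 1.3² = 36 × 3.026² / 1.69 = 195.05, so 98 per arm. Then 98 / 0.8 = 122.5, so 123 per arm and 246 in total. The plan's figures reproduce, so the sample size is not the problem.
- Reject limits are 4.840, 3.422, 1.874 and accept limits 0.020, 0.506, 1.874. Power at 98 per arm is 80.2%.

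**2. What the texts imply together.**
- Stated consequences of missing data: FAS exclusion if there are no post-dose data at all, and PP exclusion under item 9.
- Not stated: how a FAS patient with some post-dose data but no Day-90 MoCA is analysed.
- The number of such patients is not given. The 20% withdrawal allowance does not supply it: it is worded as a minimum, is counted from consent, and covers every reason for not completing per protocol, including screening failure.

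**3. Hypothetical shifts.** The loss rates and gaps below are assumptions with no source in the documents. Let p be the fraction lost and g the completer mean minus the withdrawn-patient mean, for active (A) and placebo (P). Completer difference minus all-patient difference = pA·gA − pP·gP.
- 20% lost in each arm, gap 3 in both: 0.20×3 − 0.20×3 = 0
- 7.5% vs 12.5%, gap 3: 0.225 − 0.375 = −0.15
- 10% in each arm, gaps 1 vs 3: 0.10 − 0.30 = −0.20
- 15% vs 25%, gap 3: 0.45 − 0.75 = −0.30
- 20% in each arm, gaps 1 vs 3: 0.20 − 0.60 = −0.40

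Signs reverse if the arms are swapped. With 98 per arm and the boundaries above:

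| Unfavourable shift | Net difference | Power | Early acceptance of H0 |
|---|---|---|---|
| 0 | 1.30 | 80.2% | 11.4% |
| 0.15 | 1.15 | 71.0% | not computed |
| 0.20 | 1.10 | 67.4% | not computed |
| 0.30 | 1.00 | 59.7% | 18.9% |
| 0.40 | 0.90 | 51.4% | 21.8% |

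**4. Cost of follow-up off drug.** Assume that patients who stop show no drug effect. The difference becomes 1.3 × 0.9 = 1.17 if 10% stop, or 1.3 × 0.8 = 1.04 if 20% stop.

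| Observed per arm | 10% stop | 20% stop |
|---|---|---|
| 123 (best case, all dosed and observed) | about 81% | about 72% |
| 98 | about 72% | about 63% |

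If the looks stay at 30 and 60 observed values and the final number is 246, the fractions become 30/246 = 12.2% and 60/246 = 24.4%. With recomputed boundaries, power is 81.2% and 72.5%. With the planned critical values it is 78.0% and 69.4%, with two-sided error 4.8%.

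**The case against.** - **Silence in a summary is not a decision.** The text calls itself a protocol summary, and fuller text may hold these rules. The heading of the list does not say what is being withdrawn or terminated, and nowhere is a patient who stops drug said to miss Visit 4. This stands: the loss is inferred, and the supportable claim is that the rule is not stated here. Even so, the summary goes as far as PP deviations and program code, so a rule for a missing primary outcome belongs at that level of detail.
- **Observation period says patients are monitored for 90 days in total.** That matches the treatment duration. It is not an instruction to follow patients after they stop drug.
- **Repeated-measures and mixed models are named.** A likelihood model of baseline and Day-90 MoCA can keep patients with a baseline only, and is valid if loss depends on arm and baseline. But Statistical criteria ties mixed models to non-normal data and does not assign them to missing data. There is no intermediate MoCA to draw on, and such a model of MoCA alone would not use the Visit 2 NIHSS.
- **The bias figures are assumed.** This stands in full. A 3-point gap is a whole SD. The trial is double-blind with a placebo of matching description, and nothing in the documents shows unequal loss. At look 2 the acceptance zone is 0.506 × 3 × √(2/30) = 0.39 points, which is only about half the standard error of 0.77.
- **The interim restriction is partly unavoidable.** A Day-90 endpoint needs a Day-90 value. If withdrawn patients have none, completers and observed values largely coincide. The interim issue therefore follows mainly from the withdrawal rule.
- **Using off-drug data is a choice of estimand.** It is, and the dilution in step 4 is its price.

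**Conclusion.** The point holds as a gap between the withdrawal list, the MoCA schedule and the FAS definition. As the summary reads, patients can be in the FAS without the primary outcome, and their analysis is not specified. It should be fixed before the data are collected.

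A reader might go further and infer that the result will be biased, that loss will differ between arms, or that about 50 of 246 patients (246 − 196) will lack a MoCA in the FAS. The documents support none of these. Bias is zero if loss and gaps match between arms, its direction is unknown, and some of the 50 may never enter the FAS. The 0.15 to 0.40 point shifts, with power of about 71% to 51%, show only what assumed imbalances would do. Confidence is medium, because the reading rests on a summary.

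**What to change.** Leave the rules for stopping study drug unchanged.

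1. State that stopping study drug or starting a prohibited medicine does not by itself end follow-up. Unless consent is withdrawn, the already planned Visit 4 assessments, including MoCA, are done at Day 90 for every randomized, dosed patient.
2. Analyse the FAS by randomized arm with all observed Day-90 MoCA values. Trigger the looks on 30 and 60 observed values instead of completers, and recompute the boundaries if the final number differs from 196.
3. As supporting detail, name the primary set and prespecify one missing-MoCA method. One acceptable option is multiple imputation from arm, baseline MoCA, NIHSS at Visits 1 and 2 and drug-stopping status. Add a tipping-point sensitivity analysis, and report missingness (with reasons) and deaths by arm.

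The cost is wording, plus a scheduled visit for patients who stop drug. The downside is the dilution in step 4 of the working. The plan should state that loss of power instead of enrolling more patients to offset it. If fuller protocol text already has these rules, carrying them into the summary is enough.
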